7. ADVERSE EVENTS AND REPORTING PROCEDURES

7.1 Potential Adverse Events

The most common adverse reactions ($\geq 2\%$) following administration of Ferumoxytol are diarrhea, nausea, dizziness, hypotension, constipation and peripheral edema. Ferumoxytol may cause serious hypersensitivity reactions including anaphylaxis and/or anaphylactoid reactions. In clinical studies, serious hypersensitivity reactions were reported in 0.2% of subjects receiving Ferumoxytol. Hypotension may follow Ferumoxytol administration. In clinical studies, hypotension was reported in 1.9 % of subjects.

7.2 Adverse Event Reporting

In an unanticipated and unlikely event of any adverse event or anaphylactoid reaction to this contrast agent, appropriate actions will be taken to treat the reaction and the event will be reported to the IRB.

8. STUDY CALENDAR :

	Pre study	Initial MRI	24 hour delayed MRI
Complete medical history	X		
Physical Examination	X		
Vital Signs (Heart rate, respiratory rate, blood pressure, temperature)	X	X	
Height	X		
Weight	X	X	
ECG	X		
Pregnancy Test (B-HCG)	X		
Informed consent	X		
Investigational agent administration		X	
Adverse event evaluation		X	X
MRI exam evaluation		X	X

9. MEASUREMENT

9.1 Primary Outcome measures

Primary outcome: To determine contrast enhancement characters on T1 (immediate post contrast) and T2 (24 hours) weighted MR images, of bone sarcoma and osteomyelitis.

9.1.1 Relevant Subset

The outcome will be measured on all subjects included in the study.

9.1.2 Measurement Definition

To define distinctive MR signal characteristics of bone sarcomas and osteomyelitis.

Qualitative measurement: An initial precontrast scan of the lesion will be obtained to evaluate the lesion. This will serve as an internal control to define the postcontrast effects. Following administration of contrast agent ferumoxytol, post contrast MR images will be obtained and enhancement characteristics of the lesion will be assessed visually in comparison with the precontrast scan. The following pulse sequences will be applied: Long axis T1-spin echo (SE) images and short TI inversion recovery (STIR) images, covering the whole bone from joint to joint, axial T2-weighted fat-saturated fast spin echo (FSE) images focusing on the bone lesion, dynamic contrast-enhanced T1-weighted 3D spoiled gradient recalled echo (SPGR) images, and axial multi-echo T2*-weighted gradient echo (GE) images.

Quantitative measurement: Signal Intensity of the lesion and internal controls will be measured by operator defined ROI. Contrast enhancement and signal to noise ratios will be calculated. T2- and T2* relaxation times and R2 and R2* relaxation rates of the bone lesions will be calculated based on multiecho T2 weighted sequences.

9.1.3 Measurement Methods

Primary outcome of these examinations is to define distinctive MR signal characteristics of bone sarcomas and osteomyelitis, which will be immediately applicable in a clinical setting.

The MR signal intensity of the bone lesion, bone marrow, adjacent normal muscle, and background noise will be measured by operator defined regions of interest (ROI). The contrast enhancement of the bone lesions will be calculated as $(SI_{post}/SI_{pre})/SI_{pre} \times 100\%$. The bone marrow will serve as a positive internal standard to confirm contrast accumulation at the target site and muscle will serve as a negative standard (no enhancement expected). Serial signal-to-noise ratios of the lesion on dynamic postcontrast T1-SPGR sequences will be used to calculate the blood volume of the lesion and microvascular permeability of ferumoxytol via kinetic analyses as described previously.

9.1.4 Measurement Time Points:

Data analysis of the initial MR scan and 24hr Delayed MR scans will be performed

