2.4 Study Design

Diagnostic: The goal of our project is to establish a novel, non-invasive, immediately clinically applicable imaging test for the differentiation of bone sarcomas (osteosarcomas and Ewing sarcomas) and osteomyelitis. Our approach relies on the FDA-approved iron supplement drug ferumoxytol (Feraheme), which is used in patients for intravenous treatment of iron deficiency. Ferumoxytol is composed of iron oxide nanoparticles, which provide a strong T1- and T2-signal on magnetic resonance (MR) images and, thus, can be used as an MR contrast agent. Based on our extensive experience with pre-clinical and clinical imaging applications of iron oxide nanoparticles, we hypothesize that MR image after intravenous injection of ferumoxytol will demonstrate a significantly stronger T1- and T2- enhancement of osteomyelitis when compared to malignant bone sarcomas.

Hypotheses:

(1) *Bone sarcomas and osteomyelitis show a different T1-enhancement at 1 h post injection (p.i.) of ferumoxytol*

(2) *Bone sarcomas and osteomyelitis demonstrate differences in T2-enhancement at 24 h p.i. of ferumoxytol*

We plan to enroll 20 patients in this study, 10 patients with bone sarcomas and 10 patients with an osteomyelitis. The sample size has been determined based on our preliminary data and power calculations. We will screen all patients with proven or suspected bone sarcoma or osteomyelitis for potential participation in this study. Inclusion criteria will comprise an age of 10-21 years (we do not include younger patients in order to exclude need of sedation) and a suspected or confirmed diagnosis of a bone sarcoma or osteomyelitis. Exclusion criteria comprise MR-incompatible metal implants, need of sedation (since an anesthesia is not supported by this), claustrophobia or hemosiderosis/hemochromatosis. All patients will undergo two subsequent imaging tests on a 3T MR scanner, using dedicated surface coils for high resolution MR imaging. During the first MR examination, ferumoxytol will be injected intravenously at a dose of 5 mg Fe/kg:

(A) MRI before and up to 1 h after injection of ferumoxytol for evaluation of lesion perfusion, blood volume, microvascular permeability and interstitial retention (enhanced permeability and retention effect of macromolecules)

(B) 24h after (A): Follow up MRI for evaluation of macrophage phagocytosis

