2.5 Correlative Studies Background

Our group has worked on MR imaging techniques with iron oxide nanoparticles since 1995 (11-24). We and others have found that intravenously injected USPIO with diameters in the order of 20-50 nm cause a long lasting, positive “blood pool” or vascular enhancement on T1-weighted MR images (9,14,19). In pathologies with an increased microvascular permeability, USPIO extravasate into the interstitium and cause a T1-effect of

the target tissue, which is strongly dependent on the proton content of the interstitial space (among other technical factors). We have thoroughly investigated various factors that lead to an optimized tissue T1-enhancement of USPIO (9, 14, and 19). We have shown that malignant lesions in the bone marrow of patients show nearly no USPIO T1-enhancement, presumably due to their high cellularity, small intercellular space and low proton content (Fig. 1). Inflammations, on the other hand, show a strong T1-enhancement, presumably due to the edematous, proton rich environment (Fig. 2). These data suggest that tumors and inflammations may demonstrate differences in T1-enhancement.

USPIO in the interstitium are subsequently slowly phagocytosed by macrophages in various target tissues, such as liver, spleen, bone marrow or macrophage containing pathologies, where they primarily cause a negative (dark) signal effect on T2-weighted MR images (11,13,18,19,24). Focal malignant tumor lesions in organs of the RES (reticulo-endothelial system) contain no or very few macrophages, thus do not phagocytose USPIO, and stand out as bright lesions (Fig. 1). However, macrophage rich inflammations cause a marked signal loss on delayed T2-weighted MR images (Fig. 2). Thus, we have evidence from a variety of pre-clinical and clinical investigations, that tumors and inflammations may show distinct T2-enhancement patterns.

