Of note, the PI of this proposed study has applied USPIO as MR contrast agents in phase II and III clinical trials in adult patients (11, 13, 14, and 20). These contrast agents are very well tolerated and show excellent safety profiles (5-8). The delivered iron dose via a typical ferumoxytol administration is in the order of 150-500 mg iron oxides (note that these are coated iron particles, not free iron), which is equivalent to or lower than the iron dose administered with one blood sample. USPIO are slowly metabolized in the liver and not excreted via the kidneys. Thus, they are safe to use in patients with renal insufficiencies and are not associated with any risk of nephrogenic sclerosis (a potential adverse event after injections of certain gadolinium chelates). Anaphylaxis or anaphylactoid reactions were reported in 0.2% of a subject, which is in the order of or lower compared to other MR contrast agents (see FDA report, ref. 6).

Figure 1: MR signal characteristics of bone marrow tumors with USPIO, as demonstrated in a patient with Non-Hodgkin's lymphoma after chemotherapy and GCSF therapy. (A) T1-weighted MR images before contrast media administration show a hypercellular reconverted bone marrow, which demonstrates diffusely decreased signal due to its high cellularity. Two focal lesions are noted (arrows). (B) T1-weighted MR images after intravenous administration of the USPIO ferumoxtran-10 (Sinerem / Combidex) do not show any T1-enhancement (positive contrast) of these lesions. (C) Precontrast STIR images show a relatively high signal of the hypercellular reconverted bone marrow with focal, more hyperintense lesions (arrows). (D) STIR images after intravenous administration of ferumoxtran-10 show a marked, diffuse T2-enhancement (negative contrast, signal loss) of the normal bone marrow due to phagocytosis of the agent by macrophages in normal bone marrow. Focal neoplastic lesions (arrows) contain no or few macrophages and stand out as bright lesions (arrows).

[figure not shown]
[figure not shown]

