6. DOSE MODIFICATIONS

Dose modification scheme:

- (A) Serious anaphylactoid reactions are not dose dependent. Thus, in case we should observe an increased incidence of severe anaphylactoid reactions, i.e. more than one patient in our limited study population of 20 patients, or if any of our patients encounters a permanent impairment due to the ferumoxytol administration, the study will be terminated.
- (B) In case we should observe an unexpected decrease in blood pressure of more than 10% in more than one patient via blood pressure measurements or in case we observe severe nausea in more than one patient, we will successively decrease the administered dose by 1 mg/kg until event-free tolerance is achieved. Of note, our colleagues from Oregon Health & Science University (see below) reported no such side effects of ferumoxytol in their population of children with brain tumors.
- (C) Precontrast MR scans will serve as an internal standard. We will measure the signal intensity of sarcomas and osteomyelitis and divide this signal by the signal of normal muscle to normalize for potential MR spectrometer variations over time. We expect at least 20% tumor/muscle enhancement on post-contrast T2-weighted MR scans compared to precontrast scans. If this enhancement will not be achieved, but ferumoxytol is well tolerated, we will increase the administered dose to 6 mg Fe/kg with a maximum total amount of 510 mg Fe (FDA-approved dose for single injection).

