- (D) In the unlikely event, that the T1- and T2-enhancement of both pathologies exceeds 500%, we have reached a plateau of contrast agent accumulation for both pathologies rather than depicting an expected relative limited accumulation of ferumoxytol in sarcomas compared to osteomyelitis. Based on our experience with pre-clinical and clinical iron oxide applications, we expect that maximal difference between sarcomas and osteomyelitis occur with the highest dose. This is the reason why we limit our study population to this dose for this initial pilot study. In the unlikely event that contrast agent accumulation reaches a plateau in both of these pathologies or no enhancement is noted on MR scans, we will terminate the study after evaluation of n=6 patients (MR data from n=6 patients should allow evaluation of significant differences between quantitative pre- and post-contrast signal intensities via a t-test). We have submitted an R21 NIH grant proposal which would allow more extensive evaluation of patient subgroups (n=5), examined with decreasing ferumoxytol doses.

Stopping rules for an individual test:

- (A) To avoid paravasal injections, the peripheral venous access will be checked with a saline flush prior to contrast media injection. In case of any swelling or discoloration at the ferumoxytol injection site (in the extremely rare event of a paravasal injection despite prior uncomplicated saline injection), the ferumoxytol injection will be stopped immediately, a new peripheral venous access will be placed at the contralateral extremity and the remaining ferumoxytol will be slowly administered. In case a local reaction is observed again, the ferumoxytol injection will be discontinued completely.

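### As it appears in the text, the only enhancement formula for the primary outcome (Section 9.1.3) is not a percent change and does not fit the 20% and 500% levels in Section 6

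*Combined protocol and SAP*

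**What the plan says.** Section 9.1 of the combined protocol and SAP sets the primary outcome: "To determine contrast enhancement characters on T1 (immediate post contrast) and T2 (24 hours) weighted MR images", for the two diseases. Section 9.1.3 defines the quantity: "The contrast enhancement of the bone lesions will be calculated as $(SI_{post}/SI_{pre})/SI_{pre" (the quote stops inside the last subscript; the expression then closes and is multiplied by 100%). No other section prints an enhancement formula. The same section names muscle as the negative reference, in which enhancement should be absent.

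Other sections attach numbers or a direction to enhancement:

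- Section 6(C) measures lesion signal and would "divide this signal by the signal of normal muscle to normalize for potential MR spectrometer variations over time". It then sets a level: "We expect at least 20% tumor/muscle enhancement on post-contrast T2-weighted MR scans compared to precontrast scans".
- Section 6(D) considers the case that "the T1- and T2-enhancement of both pathologies exceeds 500" percent.
- Section 2.5 says that "macrophage rich inflammations cause a marked signal loss on delayed T2-weighted MR images", and its Figure 1 legend describes "T2-enhancement (negative contrast, signal loss) of the normal bone marrow".

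Section 11.2.2 summarises enhancement in each group, with the SD and CV as key estimates. It then compares the groups by the area under the ROC curve and the Wilcoxon rank sum test.

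**The concern.** A percent change from baseline has a difference inside the bracket. Here the bracket holds a ratio, which already has no units, and dividing it again by SIpre leaves a quantity in units of 1/signal. Such a number cannot be compared across patients with different baseline signal, and it has no natural zero.

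The analyses in Section 11.2.2 would use this quantity directly. The SD matters beyond this trial, because Section 11.3.2 discusses using a pooled SD to size a future study. The rank-based methods give no protection, since dividing by the square of each patient's own baseline can change the order of patients. The Section 6 levels also bear on dose and on termination of the study, so the reader has to know which measure they refer to.

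**Working it through.** **Inputs.** The formula is from Section 9.1.3, the 20% and 500% levels from Section 6(C) and 6(D), and the group sizes (10 and 10) and power figure from Section 11.3. The documents give no signal intensities, so the signals below are examples. The algebra needs no assumption.

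**The plan's own power figure.** Section 11.3.2 states 80% power for 1.33 SD. A two-sample t-test with 10 per group and two-sided alpha 0.05 (assumed; the plan states none) gives 80.3%. The figure reproduces. It is in SD units, so it does not depend on the formula.

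**Algebra.** Printed value = 100 × (SIpost/SIpre)/SIpre = 100 × SIpost/SIpre². If scanner gain multiplies both signals by g, the printed value becomes 100 × g × SIpost/(g² × SIpre²), which is the old value divided by g. The percent change, 100 × (SIpost − SIpre)/SIpre, is unaffected.

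**Examples.**

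| SIpre | SIpost | Percent change | Printed formula |
|---|---|---|---|
| 200 | 200 | 0 | 0.5 |
| 200 | 160 | −20 | 0.4 |
| 200 | 240 | +20 | 0.6 |
| 200 | 300 | +50 | 0.75 |
| 400 | 600 | +50 | 0.375 |
| 200 | 1,200 | +500 | 3.0 |
| 100 | 120 | +20 | 1.2 |
| 300 | 450 | +50 | 0.5 |

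- Gain: 200 to 300 and 400 to 600 are the same +50%, yet read 0.75 and 0.375.
- Zero: unchanged tissue at 200 reads 0.5, against the expectation for muscle in Section 9.1.3.
- Sign: a 20% loss reads 0.4. No signal loss can read negative.
- Rank: 100 to 120 (+20%) scores 1.2 and 300 to 450 (+50%) scores 0.5, so the order is reversed.

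**Fit to Section 6.** At SIpre 200, a printed value of 20 needs SIpost = 20 × 200²/100 = 8,000 (40-fold), and a value of 500 needs 200,000 (1,000-fold). Conversely, a true +20% reads as 20 only if 120/SIpre = 20, so SIpre = 6. A true +500% reads as 500 only if 600/SIpre = 500, so SIpre = 1.2. No single baseline fits both levels.

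Lesion/muscle ratios as inputs do not rescue the formula. With a pre-contrast ratio of 1, no change reads 100 and +20% reads 120; with a ratio of 2, they read 50 and 60. With a minus sign, a 1.2-fold signal gives 20%, a 6-fold signal gives 500% and no change gives 0, at any baseline.

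**What remains with a minus sign.**

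- Section 9.1.3 uses lesion signal alone, while Section 6(C) divides by muscle. As a chosen example, lesion +25% with muscle signal or session gain +10% is +25% on the first measure and 1.25/1.10 − 1 = +13.6% on the second. Lesion −25% with muscle −10% is −25% against 0.75/0.90 − 1 = −16.7%. The two measures can fall on opposite sides of a 20% change.
- A signed signal loss lies between −100% and 0. The 500% level therefore has no reading for T2 signal loss, and the 20% level has one only if it means the size of the loss.

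**The case against.** The strongest objection is that the whole formula point turns on one character. The expression was transcribed from PDF by a program, and a minus may have become a slash. The surrounding text also points to percent change: the multiplication by 100%, the absence of enhancement expected in muscle, and the comparison with pre-contrast scans in Section 6(C). An analyst would probably read it that way. This stands, and it is why the source check comes first and the severity is conditional. It does not remove the point, because no other section prints a formula and the definition of a primary outcome should not rest on a guess.

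It can also be said that Section 6(C) and Section 9.1.3 serve different purposes and may use different measures, and that a T2 loss of at least 20% is a natural reading given Section 2.5. Both are fair. If muscle does not enhance, the two measures differ only through changes in gain between scans. What stands is that the documents do not say which measure the Section 6 levels use, and that 500% has no meaning as a signal loss.

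A reader might infer that the trial loses a calculable share of its power. The documents do not support that. They give neither the spread of baseline signal nor its distribution in the two groups. With no baseline spread the ranks, and so the Wilcoxon result, are unchanged, and a baseline difference between groups could raise or lower the apparent separation.

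**Conclusion.** The point holds for the formula as it appears in the text. That 100 × SIpost/SIpre² is not a percent change, depends on gain, has no zero for unchanged tissue, can reverse ranks and does not fit the Section 6 levels is exact and rests on no assumption. Applied literally, it would distort the SD, CV, AUC and Wilcoxon result for enhancement by an amount that cannot be stated from the documents.

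Not affected are the T2 and T2* relaxation times and rates, the visual reads, and the stated 80% power. It would go too far to conclude that the whole primary analysis is invalid, or that the sponsor's document certainly contains the error.

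Severity: must-fix if the source page prints the slash. If it prints a minus, only the clarification of measure and sign remains, and that is minor.

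**What to change.** 1. Check the Section 9.1.3 formula against the source page. If the slash is printed, replace the expression with (SIpost − SIpre)/SIpre × 100% and refer to it in Section 11.2.2 for enhancement.
2. State the sign convention for T2 signal loss: signed change, or size of the loss. Reversing the sign only turns the AUC into 1 − AUC and flips the sign of the CV; the SD and the two-sided Wilcoxon p-value stay the same.
3. Report the SD as the main measure of spread and interpret the CV with caution. Section 2.5 reports almost no T1-enhancement in malignant marrow lesions, so the mean percent change in sarcoma may be close to zero and the CV unstable.
4. Whether or not the slash is printed, reconcile Sections 6(C), 6(D) and 9.1.3 on whether the 20% and 500% levels refer to lesion signal or lesion/muscle signal, and on how each reads for T2. No dose or stopping rule is proposed here.

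A muscle-normalised percent change may be added as an optional sensitivity analysis. It would matter mainly for the 24 h scan, because the first examination already covers "MRI before and up to 1 h after injection of ferumoxytol". Its price is that measurement noise in the muscle region enters both before and after contrast.

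The cost is one formula, one sentence on sign, a cross-reference and a clarification in Section 6. No new data are needed, since lesion and muscle signals are already to be measured.

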Since ferumoxytol is a “blood pool agent” (i.e. providing long lasting vascular enhancement), it is not crucial for the quality of the imaging scan to administer the contrast agent while the patient is in the scanner or to start a post-contrast scan immediately after contrast media administration. Thus, we will hand-inject ferumoxytol slowly into a peripheral vein while the patient is outside of the MR scanner and under direct supervision. We will observe the patient for a few minutes, acquire vital signs and ask him/her for any subjective adverse effects before we continue the imaging scan. We will continue to observe the patient closely and record heart rate and respiratory rate continuously during the MR scan. Blood pressure and temperature will be monitored before, directly after contrast media injection as well as at the end of the MR scan. The patient will be monitored up to 90 minutes after the contrast media administration. These data will be recorded according to the following table, which is part of the case report form:

Patient Name:	Patient weight:						
Birth Date:	Ferumoxytol dose (5 mg/kg):						
Medical Record #:	Ferumoxytol volume: = weight (kg) x dose (5 mg Fe/kg) / 30 mg Fe/ml						
Ferumoxytol injection, date (dd/mm/yyyy) and start time (hh/min):							
Ferumoxytol injection end time (hh/min):							
Planned injection rate: 10 ml / min	Actual injection rate:						
Contrast agent completely injected: yes / no	Actual injection volume:						
Evidence of paravasal injection: yes / no	Local Reaction at injection site: yes / no						
Vital signs:	pre	0 min	15 min	30 min	45 min	60 min	90 min
Heart Rate							
Respiratory rate							
Blood pressure							
Temperature							
Any objective or subjective adverse reaction (time):							
Any objective or subjective adverse reaction (describe):							

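### Section 9.1.3 computes enhancement from lesion signal alone, without the muscle normalisation of Section 6(C); secondarily, the lesion perfusion listed in Section 2.4(A) cannot be measured with the injection timing in Section 4

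*Combined protocol and SAP*

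**What the plan says.** **Enhancement.** Section 9.1.3 measures signal in operator-defined regions for lesion, bone marrow, adjacent muscle and background noise. Its enhancement formula uses only the lesion's SI_pre and SI_post. Muscle is named as a negative standard but does not enter the formula. Section 6(C), which governs dose changes, takes the signal of sarcomas and osteomyelitis and would "divide this signal by the signal of normal muscle to normalize for potential MR spectrometer variations over time". Its 20% criterion for post-contrast T2 is a tumour/muscle quantity.

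**Scans compared.** Sections 2.4 and 4 describe a first exam (before and up to 1 h after injection) and a second, separate exam 24 h later without new contrast. Within the first exam, staff "hand-inject ferumoxytol slowly into a peripheral vein while the patient is outside of the MR scanner". Then: "We will observe the patient for a few minutes, acquire vital signs", after which imaging continues.

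**Perfusion and kinetics.** Section 2.4(A) says that the first exam is "for evaluation of lesion perfusion, blood volume, microvascular permeability and interstitial retention". Section 9.1.3 is narrower. There, repeated lesion signal-to-noise values from the dynamic T1 series "will be used to calculate the blood volume of the lesion and microvascular permeability of ferumoxytol via kinetic analyses".

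**Analysis.** Section 11.2.2 summarises enhancement and relaxation times in each group, with the SD and the coefficient of variation as the main estimates. It also plans an ROC area and a Wilcoxon test. Kinetic parameters are not named there.

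**The concern.** The protocol recognises that scanner signal can drift between scans and corrects for it in the dose rule, but leaves the correction out of the formula for the primary outcome. An uncorrected ratio mixes biology with any change in gain, coil loading or position between the two scans. For the delayed T2 outcome the two scans always come from different exams on different days.

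In a pilot with 10 patients per group, this matters most for the spread. Section 11.3.2 wants a pooled SD for planning later studies. Scanner variance that could have been removed would enlarge that SD and the CV, and blur the separation between the groups.

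Separately, first-pass perfusion needs images while contrast arrives. If injection and observation are finished before imaging resumes, that phase is not recorded in any patient handled as written.

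**Working it through.** **1. The plan's own figures.** None concerns this point directly, but those in Section 11.3.2 rest on the SD. A two-sample t-test with 10 v 10, difference 1.33 SD, 18 df and an assumed two-sided alpha of 0.05 gives power 80.3% (stated: 80%). The probabilities of underestimating a future sample size reproduce too: P(χ²₁₈ ≤ 18 × 0.8 = 14.4) = 29.7% (stated: 30%) and P(χ²₁₈ ≤ 18 × 0.5 = 9) = 4.0% (stated: 4%). They describe sampling error in the SD and say nothing about measurement variance inside it.

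**2. Effect of a shift on the unnormalised value.** As printed, the 9.1.3 formula has a division sign where a relative change needs a minus. This may be a typing or text-extraction artefact, so I assume (SI_post − SI_pre)/SI_pre. Let e be the true enhancement and g the factor by which set-up or gain changes the later scan:

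apparent enhancement = (1 + e) × g − 1

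The documents give no value for g, so the range is assumed. For e I use 20%, only as a convenient size taken from 6(C).

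| g | e = 0 | e = 20% |
|---|---|---|
| 0.90 | −10% | 1.20 × 0.90 − 1 = 8% |
| 0.95 | −5% | 1.20 × 0.95 − 1 = 14% |
| 1.05 | +5% | 1.20 × 1.05 − 1 = 26% |
| 1.10 | +10% | 1.20 × 1.10 − 1 = 32% |

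**3. Effect on the SD.** If g varies between patients around 1 with SD s, independently of e, the variance of the apparent value is at least Var(e) + (1 + mean e)² × s². With shifts of +10% or −10% equally likely, s = 0.10, and the added component is 1.20 × 0.10 = 12 percentage points, combined in quadrature with the true SD. The true SD is unknown, so the proportional inflation is too.

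**4. Effect of the muscle ratio.** Let R = lesion signal / muscle signal. If g acts on both tissues, R_post = (g × lesion)/(g × muscle) and g cancels. A true 20% then reads as 20%, provided muscle itself does not change, as 9.1.3 expects.

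**5. Perfusion and kinetics.** Section 4 gives a 1–2 min injection, then an observation period of unstated length (3–10 min assumed). Arrival is over before the first dynamic image. The slower phase remains visible: with the 15 h half-life in Section 2.2, the plasma level 2^(−t/900), t in minutes, is 99.8% at 3 min, 99.2% at 10 min and 95.5% at 60 min. Take a blood-volume-plus-leakage model, v × Cp(t) + k × ∫Cp, with 13 equally spaced samples ending at 60 min, constant noise and a known plasma curve (all assumed). Starting at 3 or 10 min instead of 0 changes the relative SE of v from 0.527 to 0.568 or 0.688 (+8% to +31%), and of k from 0.01483 to 0.01561 or 0.01779 (+5% to +20%). Precision is lost, but both stay estimable.

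**The case against.** The strongest reply is that the protocol already has the safeguards. Section 6(C) describes the muscle division in general terms, 9.1.3 measures muscle, and 9.1.2 adds signal-to-noise ratios and T2/T2* relaxation times and rates. Relaxation estimates from multi-echo data do not depend on a common gain factor, and 11.2.2 analyses them beside enhancement. This limits the problem to signal-intensity-based enhancement. It does not remove it: that enhancement is a primary measure, and its written formula has no muscle term.

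A reader might go further and infer that patients are repositioned between the same-day scans. The documents do not say so. Section 4 has the injection "while the patient is outside of the MR scanner and under direct supervision" and speaks of continuing the scan; no change of coil, position or gain is described. Repositioning is possible, no more. The separate 24 h exam is documented, but is separate wherever the injection takes place.

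A reader might also infer that the blood-volume and permeability analysis fails. Section 4 argues that a long-lasting blood-pool agent need not be imaged at once. For steady-state measures that argument holds, as step 5 shows. It does not cover contrast arrival. Perfusion appears in the purpose list of 2.4(A), not in the outcome measures of Section 9, and reading it as first-pass perfusion is an interpretation.

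Finally, the ±10% shift has no source in the documents, and it should not be set against the 20% criterion in 6(C): that criterion is already muscle-normalised, so a common shift cancels from it.

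**Conclusion.** The inconsistency between 9.1.3 and 6(C) is real and reaches the primary enhancement value, most clearly at 24 h. Its size cannot be derived; 8% to 32% for a true 20% is an illustration under an assumed ±10% shift and the relative-change reading of the formula. Random shifts would inflate the SD and CV, so a future sample size based on them would tend to be too large. The present sample size and stated power calculation are unaffected.

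The perfusion point is secondary. Sections 2.4(A) and 4 do not fit together if perfusion means first pass. The documents do not support the inference that the kinetic analysis is invalid: blood volume and slow leakage lose some precision but remain estimable, given a precontrast baseline and a blood signal. Neither is specified: 9.1.3 lists no vessel region and no precontrast SPGR baseline, and gives no citation for its kinetic method. This is a minor, easily corrected weakness.

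**What to change.** In Section 9.1.3, define R = SI_lesion / SI_muscle and compute every signal-intensity-based pre/post change, at 1 h and at 24 h, as (R_post − R_pre)/R_pre × 100%, in line with 6(C). Print the formula in full, which also settles the sign. Have 11.2.2 refer to this definition, and leave relaxation times as planned.

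In Section 2.4(A), drop lesion perfusion or reconcile it with Section 4, leaving the injection procedure unchanged. Label blood volume and slow leakage over the series up to 1 h as exploratory. If they are kept, state the precontrast SPGR baseline, a vessel region and the kinetic model.

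The cost is wording. Muscle regions are already measured and no scan is added. The ratio brings in some muscle measurement noise, removes only shifts shared by lesion and muscle, and would absorb any real muscle enhancement. Tabulating the unnormalised values alongside would let readers judge this. A vessel region would be a small extra measurement, needed only if the kinetics stay.
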